# 7.6.3 Secondary Analyses

### Acceptability

To assess acceptability of the 744LA, the proportion (with 95% CI for the 744LA arm) of subjects who would consider using 744LA for HIV prevention in the future will be calculated among all enrolled participants (including those who terminated product use during the trial) and summarized by treatment arm.

A questionnaire modeled after the HIV Treatment Satisfaction Questionnaire (HIVTSQ) will also be used to assess participant acceptability and satisfaction to the treatment. For each question the responses will be summarized by the proportion of participants reporting the response on the Likert scale out of all those that answered the question by visit and treatment arm. An overall treatment satisfaction score will be calculated for each participant by visit. These total scores will be summarized by visit and treatment arm.

#### **Sexual Risk Behaviors**

Change in sexual risk behavior (number of sexual partners, episodes of unprotected anal and/or vaginal intercourse) during the injection phase will be measured by summarizing the change from baseline by visit and treatment arm.

#### HIV Incidence

HIV incidence rate will be calculated as the total number of participants with confirmed HIV infection during study follow-up divided by the person-years accumulated in each arm. 95% CIs will be calculated based on Poisson distribution assumptions.

#### **Pharmacokinetics**

Plasma GSK1265744 concentration-time data will be analyzed by noncompartmental methods using WinNonlin Professional 5.2 or higher, Phoenix (Pharsight Corporation) or comparable software. Individual plasma PK parameters for each injection interval will be determined, including: area under the plasma concentration time curve over the dosing interval (AUC(0- $\tau$ )), maximum observed concentration (Cmax), time to maximum observed concentration (tmax), concentration at the end of the dosing interval (C $\tau$ ), apparent terminal phase half-life for 744LA administration (t $\tau$ ) and lambda z as a measure of absorption rate constant ( $\lambda$ z) if data allow.

Descriptive statistics will be used to summarize GSK1265744 concentration by time and plasma PK parameters. Unless stated otherwise, descriptive summaries will include n, mean, standard deviation (SD), coefficient of variation (%CV), median, minimum, and maximum for continuous variables, n and percent for categorical variables, and geometric mean, 95% confidence interval (CI), and the between-subject CV (%CVb) for the loge-transformed PK parameters.

Accumulation of GSK1265744 will determined by using point estimates and confidence intervals for difference in least squares means for the comparisons of  $AUC_{(0-\tau)}$ ,  $C_{max}$ , and  $C_{\tau}$  as follows:

Table 7: Summary of Comparisons of AUC(0- $\tau$ ), Cmax, and C

Comparison	Test	Reference
	$AUC(0-\tau)$ , third injection (Week 29 -	AUC(0-τ), first injection (Week
	41)	5-17)
Accumulation	C max , third injection	C max , first injection
	$C_{\tau}$ , third injection (Week 41)	$C_{\tau}$ , first injection (Week 17)

The difference in pharmacokinetic parameters,  $AUC_{(0-\tau)}$ ,  $C_{max}$ , and  $C_{\tau}$ , between the two different time points will be tested using paired t-test if the data or log transferred data appear to be normally distributed and using Wilcoxon signed rank test if the data or log transferred data are not normally distributed.

Time to steady state will be assessed by comparing plasma concentration at Week 41 ( $C_{\tau}$  following third injection) to previous  $C_{\tau}$  concentrations at Weeks 17 and 29. This may be accomplished by visual inspection of graphical data or by calculating the point estimate and confidence interval for the slope for  $\log(C_{\tau})$  by week for Weeks 17 through 41.

Injectable Hormonal Contraception Usage

Safety and Tolerability analyses described above will be performed on the subset of female participants who self-report the use of injectable hormonal-based contraception at study entry or at any time during the study period. Proportions of such women meeting safety or tolerability endpoints will be compared a) across study arms b) to women in the active study arm who are do not report the use of injectable hormonal contraception c) to the overall study population randomized to active GSK1265744.

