#### 744LA dosing:

Following a single IM or SC injection of 744LA, plasma drug concentrations increased rapidly over the first week, followed by a general trend to plateau for the remainder of the 12-week follow-up period. GSK1265744 was detected in plasma up to 48 weeks. When the dose was administered as two equally divided injections, total drug release was increased so that  $C_{max}$  was greater than dose proportional and there was a more pronounced decay in drug concentrations over time. However, overall extent of exposure (AUC $_{0-\infty tau}$ ) was similar. Following single dose 744LA administration, mean absorption-limited apparent terminal phase half-life ranged from 21 to 50 days, reflecting elimination from the depot site (absorption from depot site) rather than the systemic circulation.

744LA PK has been evaluated following repeat administration in healthy HIV-uninfected subjects. Following a loading dose of 800 mg IM and three monthly (every 28 days) maintenance doses, the third monthly 200 mg SC, 200 mg IM and 400 mg IM injections achieved geometric mean plasma  $C_{tau}$  of .61µg/mL, 1.72 µg/mL, and 3.22 µg/mL – 9.7-, 10-, and 19-fold above the PA-IC90 (0.166 µg/mL), respectively. Following two quarterly 800 mg IM doses, geometric mean plasma GSK1265744  $C_{tau}$  was 1.11 µg/mL, 6.7-fold above the PA-IC90.

The rationale for extended follow-up in this study (52 weeks after last injection) is two-fold: The first is to assess safety events during the prolonged interval during which drug levels have been demonstrated to be detectable in blood plasma in order to best characterize the safety profile of 744LA. The second is to characterize in detail any HIV infections which might occur during a period of declining blood plasma drug levels, including viral resistance profiles and response to antiretroviral therapy treatment.

Plans for suppressive ART treatment of on-study incident HIV serconversions are detailed in Section 5.17.

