#### **5.24** Pharmacokinetics

Blood samples will be collected during the oral lead-in phase of the study for determination of plasma concentrations of GSK1265744 following oral dosing. Blood samples for PK analysis will also be collected starting on the first day of the first injection phase prior to the injection and every visit thereafter, as indicated in Appendices I-III. At each injection visit a blood sample will be collected prior to the injections at Weeks 5, 17 and 29, and one week post-injection at Weeks 6, 18, and 30, and 12 weeks post-injection at Weeks 17, 29, and 41. The sample collected 12 weeks following each injection will serve as the pre-dose sample for the subsequent dosing interval (except for after the 3rd injection visit, i.e., the sample will be collected, but will not serve as a pre-dose sample because injections will be completed after the 3rd injection). Two additional samples will be collected 4 and 8 weeks after the first injection (Weeks 9 and 13), and one additional sample will be collected 6 weeks following the second and third injections (Weeks 23 and 35). PK samples will be collected during the oral phase at Week 2 and 4, and every 12 weeks during the follow-up phase at Weeks 35, 53, 65, 77 and 81 until participants reach 52 weeks post-third injection (these collections are modified for participants who receive only one or two injections [see Appendices II and III]).

The actual date and time of each blood sample collection will be recorded, as well as the time of each injection. The timing of PK samples may be altered and/or PK samples may be obtained at additional time points to ensure thorough PK monitoring. Details of PK blood sample collection (including volume to be collected), processing, storage and shipping procedures are provided in the SSP Manual.

Concentrations of GSK1265744 will be determined in plasma using an approved, validated analytical methodology.

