# 7.0 STATISTICAL CONSIDERATIONS

# 7.1 Review of Study Design

This is a Phase IIa, randomized, multi-site, two-arm, double-blinded study of the safety, tolerability, pharmacokinetics and acceptability of 744LA. Eligible participants will be randomized 3:1, stratified by gender, to receive GSK1265744 or matching placebo. Participants will receive daily 30 mg oral 744 tablets or matching placebo for 4 weeks, followed by a one week washout period, to assess for safety and tolerability prior to receiving injections. Following clinical review of safety lab assessments from the oral regimen phase, participants will enter the injection phase and receive IM injections of 744LA or placebo at three time points at 12 week intervals. IM injections will consist of 800 mg of 744LA or a matching vehicle control, and administered as two 400 mg injections. Participants in the active drug arm will be followed for 52 weeks following their last injection. Participants in the placebo arm will be followed until 52 weeks after their last injection or until the last participant in the active study product arm completes their Week 41 visit, whichever comes first, at which time the study will be unblinded to assess the primary endpoint. When all procedures related to unblinding are completed, participants in the placebo arm will no longer be followed.

176 participants will be randomized 3:1, stratified by gender, as follows:

Arm 1: 132 participants will receive daily oral GSK1265744 (30 mg tablets) for 4 weeks, followed by a one week washout period, to establish safety and tolerability, followed by two IM administered injections of 400 mg (800 mg total) of 744LA at three time points at 12-week intervals as: Week 5, Week 17, and Week 29.

Arm 2: 44 participants will receive daily oral matching placebo and IM injections of vehicle-matched placebo on the same schedule as Arm 1.

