# 7.2 Sample Size

We expect at least 160 (120 in 744LA and 40 in placebo) out of 176 participants who will complete the primary endpoint visit (week 41) assuming the annual retention rate to be approximately 90%. The following power calculations are based on the sample size of 160 (120 in 744LA and 40 in placebo).

The goal of the safety evaluation for this study is to identify safety concerns associated with 744LA. The ability of the study to detect SAEs (See Section 6.3) can be expressed by the true event rate above which at least 1 SAE would likely be observed and the true event rate below which no events would likely be observed. Specifically, for the 744LA arm of the study (n =120), there is a 90% chance of observing at least 1 event if the true rate of such an event is 2% or more, and there is a 90% chance of observing no events if the true rate is <0.1%. For the placebo arm (n=40), there is a 90% chance of observing at least 1 event if the true rate of such an event is 5.6% or more, and there is a 90% chance of observing no events if the true rate is 0.2% or less.

Probabilities of observing 0, 1 or more, and 2 or more events among the arms (N=160; 120 in 744LA arm, and 40 in placebo arm) are presented in Table 3 for a range of true adverse event rates. These calculations provide a more complete picture of the sensitivity of this study design to identify potential safety concerns with 744LA.

Table 3: Probability of observing 0 events, 1 or more events, and 2 or more events, among both arms: the 744LA arm (n=120) and the placebo arm (n=40), for different true event rates.

True event						
rate (%)	Pr(0/120)	Pr(1+/120)	Pr(2+/120)	Pr(0/40)	Pr(1+/40)	Pr(2+/40)
0.5	54.8	45.2	12.2	81.8	18.2	1.7
1	29.9	70.1	33.8	66.9	33.1	6.1
2.5	4.8	95.2	80.5	36.3	63.7	26.4
5	0.2	99.8	98.4	12.9	87.1	60.1
10	< 0.1	>99.9	>99.9	1.5	98.5	92
15	< 0.1	>99.9	>99.9	0.2	99.8	98.8

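### The optional slope of log trough over Weeks 17 to 41 gives the Week 29 trough zero weight, so it cannot show whether a plateau was reached by Week 29

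*Protocol*

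**What the plan says.** The aim is set out in Protocol section 7.6.3, Pharmacokinetics: "Time to steady state will be assessed by comparing plasma concentration at Week 41", that is, the trough after the third injection, with the troughs at Weeks 17 and 29. Two routes are permitted, not required: "by visual inspection of graphical data or by calculating the point estimate and confidence interval for the slope for" log trough "by week for Weeks 17 through 41".

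Section 5.24 places the trough samples "12 weeks post-injection at Weeks 17, 29, and 41". Section 7.1 gives the injections "at three time points at 12-week intervals as: Week 5, Week 17, and Week 29".

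Table 7, in the same part of section 7.6.3, already compares the Week 41 trough with the Week 17 trough as a measure of accumulation. Trough concentration is also derived for each injection interval and summarised descriptively, with geometric mean and 95% confidence interval. The text names no numerical contrast between Week 41 and Week 29, and no rule for reading the slope.

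**The concern.** Time to steady state is a question about where the rise stops. With three troughs there are two steps to look at, Week 17 to 29 and Week 29 to 41, and the second shows whether the third injection still raised the trough. A straight line through three equally spaced points collapses both steps into one number, which depends only on the two ends. The slope is the only inferential method the text names for this aim, yet its estimate leaves out one of the two comparisons the aim calls for and repeats the other, which Table 7 already covers.

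At stake is the interpretation of a descriptive PK result: an analyst who takes the slope route learns how far the trough moved between the first and third injections, but not when it stopped moving.

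**Working it through.** The protocol gives no figure for this analysis, so there is none to reproduce. The check starts from the design.

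**Inputs.** Trough weeks 17, 29 and 41 (section 5.24). Dosing interval 12 weeks = 84 days (section 7.1). Half-life for illustration: "mean absorption-limited apparent terminal phase half-life ranged from 21 to 50 days" (section 1.2.4, 744LA dosing). Participants on active product at Week 41: 120 (section 7.2: "We expect at least 160 (120 in 744LA and 40 in placebo) out of 176 participants"). The within-participant SD of log trough is not in the document; 0.3 to 0.5 is assumed, for illustration only.

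**Slope weights.** The weight of each trough is (t − mean t)/Σ(t − mean t)². The mean is 29, the deviations are −12, 0 and +12, and the sum of squares is 288. The weights are −12/288 = −1/24, 0 and +12/288 = +1/24. So

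slope = (log C41 − log C17)/24.

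The Week 29 weight is also zero under generalised least squares with compound symmetry, AR(1), or random intercept plus random slope, given complete data.

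**Different profiles, same slope.** Each profile below has C41/C17 = 1.4, so each slope is ln(1.4)/24 = 0.0140 per week.

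| Relative troughs, Weeks 17, 29, 41 | C41/C29 | Slope per week |
|---|---|---|
| 1, 1.40, 1.40 (plateau by Week 29) | 1.00 | 0.0140 |
| 1, 1.18, 1.40 (steady log-linear rise) | 1.18 | 0.0140 |
| 1, 1.00, 1.40 (late rise) | 1.40 | 0.0140 |

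**Size under superposition.** Let r = 2^(−84/half-life). Successive troughs are proportional to 1, 1 + r and 1 + r + r², and the steady-state trough to 1/(1 − r).

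| Half-life | r | Week 29/17 | Week 41/29 | Share of steady state, Weeks 17, 29, 41 | Slope per week |
|---|---|---|---|---|---|
| 21 days | 0.0625 | 1.0625 | 1.0037 | 94%, 99.6%, 99.98% | 0.0027 |
| 50 days | 0.3121 | 1.312 | 1.074 | 69%, 90%, 97% | 0.0143 |

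**How clear the slope would look.** Its standard error is SD/√(288n). The less favourable end of the assumptions is SD 0.5 and n = 100: 0.5/√28,800 = 0.00295. At 50 days the slope is then 0.0143/0.00295 ≈ 4.9 standard errors above zero. At 21 days the more favourable end (SD 0.3, n = 120) gives 0.3/√34,560 = 0.00161, and 0.0027/0.00161 ≈ 1.7 standard errors. The clearly positive slope thus belongs to the long end of the half-life range.

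**What a direct contrast adds.** In 500 simulated trials per profile (n = 120, within-participant SD 0.3, C41/C17 = 1.4), the 95% interval for the slope excluded zero in every trial, both for the plateau by Week 29 and for the log-linear rise. The interval for the paired Week 41 minus Week 29 log difference excluded zero in about 5% of trials for the plateau and about 99% for the rise. The half-width of that interval is 1.96 × SD × √2/√n: 0.076 on the log scale for SD 0.3 and n = 120, and 0.139 for SD 0.5 and n = 100. That is about 8% to 15% on the ratio.

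**Departures from the ideal case.** With sampling times varied by up to one week, the Week 29 weight stays within about 8% of the end weight. With 10% or 20% of Week 41 troughs missing it is about 5% or 11%. One assumed covariance with unequal variances gave weights −0.030, −0.024 and +0.054, so a larger Week 29 weight is possible. Even then the plateau profile gives 0.336 × (0.0536 − 0.0238) = 0.0100 and the log-linear rise still 0.0140: both positive, with nothing in the number to say which profile produced it.

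**The case against.** Several points against this stand and limit it.

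- The slope is optional. The other route, visual inspection, uses the Week 29 trough, and the descriptive summaries report each interval's trough with a confidence interval. A reader might infer that the protocol cannot assess time to steady state at all. The text does not support that: only the slope route fails.
- The slope is not wholly uninformative. If troughs can only rise, a slope near zero with a tight interval would support steady state already by Week 17. At a 21-day half-life the Week 17 trough is about 94% of steady state, so this is not a remote case.
- A reader might infer that a positive slope would be reported as steady state not reached. The protocol states no such rule and no threshold.
- Time to steady state is not a listed objective (section 2.2) or endpoint (section 7.1.2). No sample size or stopping rule depends on it.
- The clearly positive slope rests on the longest half-life, on simple superposition from single-dose terminal half-lives, and on an assumed SD.
- A steady-state criterion and the details of a model may properly sit in the statistical analysis plan, which is not shown.

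What remains does not depend on those assumptions. The protocol names a specific estimator for a comparison that includes Week 29, and with complete, on-schedule data that estimator discards Week 29. This is a stated method that does not fit its stated aim, not a detail left for later.

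**Conclusion.** The point holds for the slope. With complete troughs at the nominal weeks its point estimate is exactly the Week 41 versus Week 17 log contrast divided by 24, so it repeats Table 7. It cannot distinguish a plateau reached by Week 29 from troughs still rising at Week 41. The Week 29 data still affect the width of the slope's interval through the residual variance, but they give no information on where the rise stopped.

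The zero weight is arithmetic and needs no assumption about half-life or variability. The size of any misleading impression does: under superposition it ranges from slight at 21 days (Week 41 about 0.4% above Week 29, with a small slope) to marked at 50 days (Week 41 about 7% above Week 29, with a clearly positive slope). Since the analysis is descriptive and the slope is only one of two permitted routes, the priority is low.

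**What to change.** In section 7.6.3, replace the slope with within-participant geometric mean ratios of trough, Week 41/29 and Week 29/17 (or Week 41/17, which Table 7 already covers). Estimate them on the log scale, with confidence intervals, from a paired analysis or one repeated-measures model. Keep the plots and the per-interval trough summaries as support. If steady state is to be declared formally, fix in advance the bound within which the ratio must lie; if not, report the ratios descriptively.

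The cost is one reworded sentence and one extra contrast. The samples are already scheduled, and neither the sample size nor any other analysis changes.

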### 2.2 Secondary Objectives

- Evaluate the safety and tolerability of GSK1265744 (daily oral 744 + 744LA) for 52 weeks of follow-up after final injection
- Evaluate the safety and tolerability of oral 744 from Week 0 to Week 5
- Evaluate the pharmacokinetics of 744LA administered as 800 mg IM every 12 weeks for 52 weeks of follow-up after final injection

- Evaluate differential pharmacokinetics of 744LA in participants by age, gender, race, ethnicity, weight, body mass index (BMI), and smoking status
- Evaluate the acceptability of 744LA injections
- Evaluate the effect of 744LA on sexual risk behavior by change from enrollment for repeat assessments to during the study period
- Evaluate HIV incidence and antiretroviral drug resistance, if any participants acquire HIV infection during the study
- Evaluate the safety, tolerability and pharmacokinetics of 744LA in the subset of women who use a hormone-based contraceptive

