# 7.1.2 Secondary Endpoints

- Proportion of participants who discontinue either oral or injectable study product for reasons
  of toxicity, tolerability, or acceptability prior to completion of the full oral and injectable
  phases
- Proportion of participants experiencing Grade 2 or higher clinical AEs and laboratory abnormalities during 52 weeks following final injection (safety) and any AE that leads to discontinuation (tolerability) during the aggregate oral and injectable phases
- Proportion of participants experiencing Grade 2 or higher clinical AEs and laboratory abnormalities (safety) and any AE that leads to discontinuation (tolerability) in the oral phase and washout period
- Plasma drug levels of GSK1265744 at designated time points after each injection of 744LA
- Plasma drug levels of GSK1265744 at designated time points after each injection of 744LA stratified by age, gender, race, ethnicity, weight, BMI, and smoking status
- Proportion of participants willing to use an injectable agent such as the study product for HIV prevention in the future
- Change from enrollment of self-reported sexual behavior (number of sexual partners, episodes of unprotected anal and/or vaginal intercourse) during the study period using a standardized assessment tool
- Number of incident HIV infections through the study period, including number with treatment emergent resistance
- Proportion of injectable hormonal-contraception-using female participants who reach a safety or tolerability endpoint as defined above

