# 7.6.4 Exploratory Analyses

# Pharmacokinetics/Pharmacodynamics

The relationship between GSK1265744 PK parameters and demography (age, gender, race, ethnicity, weight, BMI, smoking status) or PD endpoints (conversion to HIV-infected status, safety parameters) may be explored.

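### The hormonal-contraceptive objective covers any hormone-based method and PK, while its endpoint and analysis cover injectable users' safety and tolerability only, with one comparator containing the users

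*Protocol*

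**What the plan says.** The objective, in Protocol 2.2 and again in the Schema, is: "Evaluate the safety, tolerability and pharmacokinetics of 744LA in the subset of women who use a hormone-based contraceptive". Section 3.1 admits hormone-based contraception as a general category, and lists the intrauterine device or system as a separate item.

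The matching endpoint in 7.1.2 is: "Proportion of injectable hormonal-contraception-using female participants who reach a safety or tolerability endpoint as defined above".

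The analysis is in 7.6.3 under Injectable Hormonal Contraception Usage. It states "Safety and Tolerability analyses described above will be performed on the subset of female participants" and defines that subset as those who "self-report the use of injectable hormonal-based contraception at study entry or at any time during the study period". Their proportions are to be compared (a) across study arms, (b) "to women in the active study arm who are do not report the use of injectable hormonal contraception", and "c) to the overall study population randomized to active GSK1265744".

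On pharmacokinetics, the subgroup endpoint in 7.1.2 is "stratified by age, gender, race, ethnicity, weight, BMI, and smoking status". The exploratory analysis in 7.6.4 relates PK parameters to "demography (age, gender, race, ethnicity, weight, BMI, smoking status) or PD endpoints". Contraceptive use is in neither list, and the PK analysis in 7.6.3 does not mention it.

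**The concern.** Objective, endpoint and analysis should describe the same women and the same outcomes. Here the population narrows from any hormone-based method to injectables, and one of the three named domains, pharmacokinetics, has no endpoint or analysis. An analyst following 7.6.3 as written would leave part of a stated secondary objective unanswered.

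Two features of the analysis also distort what is reported. Comparison (c) places the active-arm users in both groups and mixes men into the reference. Defining a user by reported use at any point in the study lets post-event information decide group membership, and more follow-up gives more opportunity to be classified as a user. Section 5.19 provides contraceptive counseling and help with access throughout the study, so changes of method are foreseeable.

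**Working it through.** The protocol gives no expected number of contraceptive users and no precision for this objective, so there is no stated figure to reproduce. The first two checks compare text; the third is arithmetic on comparison (c).

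**1. Population and domains, side by side**
- Objective (2.2, Schema): any hormone-based method; safety, tolerability and PK.
- Endpoint (7.1.2): injectable methods; safety or tolerability.
- Analysis (7.6.3): injectable methods; safety and tolerability.
- PK strata (7.1.2), PK analysis (7.6.3) and exploratory PK covariates (7.6.4): contraceptive use absent.

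Women on a non-injectable hormonal method are in the group of interest under 2.2 but in the reference group under 7.6.3(b).

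**2. Timing of classification**

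The primary safety window runs from the first injection to Week 41 (7.1.1). Active-arm follow-up after three injections runs to Week 81. A woman with an event soon after Week 5 who starts an injectable contraceptive months later counts as a user with an event. Placebo participants may stop at unblinding (5.16), so some have less time in which to be classified.

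**3. Overlap in comparison (c)**

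Inputs: 132 randomized to active drug (2.4, 7.1) and about 60% women (Schema, 3.0). The share of women using injectables is not given; 30% to 50% is assumed. The group compared is taken to be the active-arm users, because 7.6.3 does not say whether placebo users are excluded from (b) and (c).
- Active-arm women: 0.60 × 132 = 79. Men: 132 − 79 = 53, and 53/132 = 40%.
- Users u: 0.30 × 79 = 24 to 0.50 × 79 = 40.
- Share of the comparator, f = u/132: 24/132 = 0.18 to 40/132 = 0.30.

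The overall rate is f × (users) + (1 − f) × (rest), so

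users − overall = (1 − f) × (users − rest),

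where the rest is everyone else in the active arm, men included. The difference is multiplied by 0.82 to 0.70, a shrinkage of 18% to 30%. An assumed true difference of 15 points would show as 15 × 0.82 = 12.3 to 15 × 0.70 = 10.5 points.

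With no true difference and event rate p, the variance of users − overall is p(1 − p)(1/u − 1/N), with N = 132. A test treating the groups as independent uses p(1 − p)(1/u + 1/N). The standard error is therefore too large by √[(1 + f)/(1 − f)]:
- f = 0.18: √(1.18/0.82) = 1.20; 1.96 × 1.20 = 2.35; true two-sided level about 1.9%.
- f = 0.30: √(1.30/0.70) = 1.36; 1.96 × 1.36 = 2.67; true two-sided level about 0.8%.

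Over a wider assumed range of 10% to 75% injectable use (8 to 59 users), f runs from 0.06 to 0.45 and the true level from about 3.7% to 0.15%. These are normal-approximation figures. They matter because the analyses carried over from 7.6.2 include Fisher's exact and chi-square tests, which assume independent groups.

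**The case against.** Four counter-arguments deserve weight.

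First, a reader might infer that none of the planned comparisons can inform the contraceptive question. The text does not support that. Comparison (a) is between arms among users, and (b) is among active-arm women with no overlap. For injectable users' safety and tolerability, both give usable descriptive contrasts. The overlap problem belongs to (c) alone.

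Second, a reader might infer that putting other hormonal users in the reference group for (b) must pull the contrast toward zero. It does so only if their methods share whatever effect injectables have, and the protocol is silent on that. For the endpoint as written, (b) is coherent.

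Third, a reader might infer that PK is where an interaction is most likely to appear. Nothing in the protocol says so; 1.2.4 describes a low potential for drug interactions. The PK gap matters because 2.2 names PK, not because an effect is expected.

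Fourth, an analysis plan could add a PK display by contraceptive use, and 7.6.2 treats p-values as descriptive. Both points stand and limit severity. They do not remove the disagreement between objective and endpoint, which are protocol content, and 7.6.3 itself fixes the user definition and comparator (c). Narrowing the objective to injectables and removing PK would also restore consistency, at the price of giving up part of the question posed.

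**Conclusion.** The point holds in this form: objective, endpoint and analysis disagree on which women and which domains are covered; the PK part of the objective has no endpoint or analysis in the protocol; comparison (c) is diluted, mixes in men and is not independent; and the definition of a user can depend on events after the outcome.

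For (c), the shrinkage is 18% to 30% and the true level of a nominal 5% independent-groups test is about 1.9% to 0.8%. Both rest on an assumed 30% to 50% injectable use among about 79 active-arm women. The test error is conservative, so (c) is more likely to hide a difference than to invent one through overlap; the effect of mixing in men could go either way. The effect of the timing rule cannot be sized from the protocol. Severity is modest, as this is one secondary objective analysed descriptively.

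**What to change.** - Align 2.2, 7.1.2 and 7.6.3 on one definition: any hormone-based method, with injectable methods as a named subgroup. State where users of a hormonal intrauterine system are counted.
- Classify women by use at the first injection (Week 5). Put those who start later in a sensitivity analysis.
- Use active-arm women not using the defined methods as the reference. Drop (c), or keep it as a descriptive display with no test. State that (b) and (c) concern active-arm users.
- Add geometric mean ratios with 95% confidence intervals for AUC(0-τ), Cmax and Cτ, users versus non-users among active-arm women.

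The cost is wording in those sections and a few more summaries. Concomitant medications are already recorded (4.4), PK samples are already collected (5.24), and the PK parameters are already derived for each injection interval (7.6.3). Section 9.2 allows PK testing to be limited to a subset of samples, so the chosen subset must support this comparison. The groups will be small and the intervals wide, so the results should be presented as descriptive.
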